7.3.1.1 Analysis of Variance

A linear mixed model for analysis of variance will be performed on the log-transformed PK parameters C_{max} and AUC following the morning product use session on each of Days 1 through 5. The model will include sequence, study product, and study day as fixed effects and subject-nested-within-sequence as a random effect. Sequence will be tested using subject-nested-within-sequence as the error term. Geometric least-squares means (LSM)- and 95% confidence intervals (CIs) will be provided for the PK parameters of C_{max} and AUC by study product. Geometric LSM ratio, 95% CIs of geometric LSM ratio, and p-values will be provided for the study product comparisons in C_{max} and AUC. The comparisons of interest will include each of the study products compared to each other.

The above statistical analyses will be performed using the appropriate SAS procedure.

Non-parametric analysis (Wilcoxon Signed Rank test) will be performed for the comparisons of T_{max}.

Details of the statistical methods will be provided in the SAP.

7.3.2 Subjective Effects

7.3.2.1 Urge to Smoke Parameters

The following parameters will be calculated for the urge to smoke assessments:

| | |
|-----------------------|---|
| Emax | The maximum change from baseline VAS score ($VAS_{preuse} - VAS_{postuse}$). |
| TEmax | Time of the Emax. If the maximum value occurs at more than one time point, TEmax will be defined as the first time point with this value. |
| AUEC ₀₋₂₄₀ | The area under the change from baseline VAS score versus time curve from time 0 to 240 minutes. |

Responses and derived parameters will be listed by subject and summarised by study product, by sex and overall using descriptive statistics.

An appropriate statistical method, similar to the PK analysis detailed above, will be used to compare Urge to Smoke parameters (no data transformation).

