HHPs will be used. Subjects will have the opportunity to see the products/devices and packaging and will participate in a Product Trial where they will take 5 puffs on a single one HTP stick (flavour chosen by subject) and 5 puffs on a single HHP stick (flavour chosen by subject). All products/devices used in the trial session will not be used in the clinical study but will be retained as demonstration samples for accountability purposes. An explanation of how the questionnaires will be administered to the subjects will be given. After the familiarisation session and completion of check-in procedures, subjects will be allowed to smoke their own cigarettes *ad libitum* but will abstain from use of any tobacco- or nicotine-containing products for at least 12 hours prior to the start of the morning controlled product use session on Day 1.

In the morning of Days 1 through 5, after pre-use assessments and confirmation of eligibility, subjects will use their randomly-assigned study product under controlled conditions by completely using a single unit (one stick, approximately 10 puffs) of the assigned study product, with puffs taken at 30-second intervals and of 3-second duration. PK samples will be collected within 5 minutes pre-study product use (timepoint '0') and at 2, 4, 6, 8, 10, 15, 30, 45, 60, 120, and 240 minutes following the start of study product use. Questionnaires will be administered to the subject at defined intervals throughout the day. Safety will be monitored throughout the day.

On Days 1 through 5, following the 4-hour PK blood collection, subjects will start a 4-hour *ad libitum* product use session (no limits on cigarette, HTP or HHP consumption) with the same study product used during the morning controlled use session.

On Days 1 through 5, puff topography will be performed over the last 2-hour period during the 4-hour *ad libitum* product use session. The Sodim Smoking Puff Analyzer Mobile (SPA-M) topography device will collect data (puff count, puff duration, puff volume, peak puff flow rate, average puff flow rate, inter-puff interval) for 2 hours. The SPA-M topography device will be reset at 60 minutes in order to collect 2 hours of data.

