## 9. SUBJECTIVE EFFECTS ASSESSMENTS

#### 9.1 Urge to Smoke (UTS)

The Urge to Smoke (visual analogue scale (VAS)) questionnaire will be completed at Time 0 (pre-product use) and at 4, 8, 15, 45, 60, 120, and 240 minutes relative to the start of controlled product use on Days 1, 2, 3, 4, and 5.

Ratings of the subjects' 'Right now, how much would you like to smoke a cigarette?' recorded on a 100 mm VAS scale ranging from "Not at all" (0) to "A great deal" (100) will be reported.

The following parameters will be calculated for the urge to smoke assessments:

Emax	The maximum change from baseline VAS score (VAS $_{preuse}$ - VAS $_{postuse}$ ).
TE max	Time of the $E_{max}$ . If the maximum value occurs at more than one time point, $TE_{max}$ will be defined as the first time point with this value.
AUEC 0-240	The area under the change from baseline VAS score versus time curve from time 0 to 240 minutes.

Baseline (VASpreuse) will be the VAS result closest and prior to product use for the respective product. Responses, change from baseline, and derived parameters will be listed by subject and summarised by product, by sex and overall using descriptive statistics (n, mean, SD, CV%, SEM, minimum, Q1, median, Q3, maximum, and 95% CI.)

A linear mixed model for ANOVA will be performed on the urge to smoke parameters (no data transformation). The model will include sequence, product, and study period as fixed effects and subject-nested-within-sequence as a random effect. Sequence will be tested using subject-nested-within-sequence as the error term for informational purposes. LSMs and 95% CIs will be provided for Emax and AUCEC0-240 by study product. LSM differences, 95% CIs of LSM differences, and p-values will be provided for the study product comparisons in Emax and AUCEC0-240. The same comparisons from PK analysis detailed above will be used.

The ANOVA analysis will be performed using the same SAS® code as outlined in the Statistical Analysis of Pharmacokinetic Parameters section above.

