#### Notes for Generating the Actual Table:

Presentation of Data:

- Median difference will be presented to 2 decimals or 3 significant figures.
- 95% CI will be presented to 4 decimals.
- p-value will be presented to 4 decimals.

The table should include all the comparisons of interest listed in Section 8.6.

----- Sample Times (Minutes)------\_\_\_\_\_ 4 8 60 Product Statistics 15 45 120 240 Sex Pre-use \_\_\_\_\_ \_\_\_\_\_ \_\_\_\_ \_\_\_\_ Α Male n Х Х Х Х Х Х Х Х n missing Х Х Х Х Х Х Х Х Mean X.X X.X X.X X.X X.X X.X X.X X.X X.XX X.XX X.XX X.XX X.XX X.XX SD X.XX X.XX CV (%) XX.X XX.X XX.X XX.X XX.X XX.X XX.X XX.X SEM X.XX X.XX X.XX X.XX X.XX X.XX X.XX X.XX Minimum XX XX XX XX XX XX XX XX Q1 X.X X.X X.X X.X X.X X.X X.X X.X Median X.X X.X X.X X.X X.X X.X X.X X.X 03 X.X X.X X.X X.X X.X X.X X.X X.X Maximum XX XX XX XX XX XX XX XX 95% CI X.X-X.X X.X-X.X X.X-X.X X.X-X.X X.X-X.X X.X-X.X X.X-X.X X.X-X.X

<Similar to above for all products and Sex = Female and Overall>

Programmer note: Table 14.2.3.1.2 will resemble the shell above but the Pre-use column will not be included.

Product A: < > Product B: < > Product C: < > Product D: < > Product E: < >

Source: ADaM.< > Program: /CAXXXX/sas\_prg/stsas/tab/programname2022Q1.sas DDMMMYYYY HH:MM

Page 1 of X Table UTSS Summary of Urge to Smoke VAS Scores Following Controlled Product Use by Sex and Product (Outcomes Population)

					Product	;	
Parameter	Sex	Statistics	A	В	С	D	E
Emax	Male	n	х	X	х	X	X
		n missing	Х	Х	Х	Х	Х
		Mean	X.X	X.X	X.X	X.X	X.X
		SD	X.XX	X.XX	X.XX	X.XX	X.XX
		CV (%)	XX.X	XX.X	XX.X	XX.X	XX.X
		SEM	X.XX	X.XX	X.XX	X.XX	X.XX
		Minimum	XX	XX	XX	XX	XX
		Q1	X.X	X.X	X.X	X.X	X.X
		Median	X.X	X.X	X.X	X.X	X.X
		Q3	X.X	X.X	X.X	X.X	X.X
		Maximum	XX	XX	XX	XX	XX
		95% CI	X.X-X.X	X.X-X.X	X.X-X.X	X.X-X.X	X.X-X.X

Table UTSP Summary of Urge to Smoke VAS Parameters Following Controlled Product Use by Sex and Product (Outcomes Population)

<Similar to above for Temax, AUCECO-240 and Sex = Female and Overall>

Product A: < > Product B: < > Product C: < > Product D: < > Product E: < >

Source: ADaM.< > Program: /CAXXXX/sas\_prg/stsas/tab/programname2022Q1.sas DDMMMYYYY HH:MM

Table SUTSP Statistical Summary of Urge to Smoke VAS Parameters Emax and AUECO-240 Following Controlled Product Use (Outcomes Population)

Parameter	n	LS Mean	95% Confidence Interval
Imax	Х	X.XXX	XX.XX - XXX.XX
AUCEO-240	Х	X.XXX	XX.XX - XXX.XX
Imax	Х	X.XXX	XX.XX - XXX.XX
AUCE0-240	Х	X.XXX	XX.XX - XXX.XX
Imax	Х	X.XXX	XX.XX - XXX.XX

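### TEmax is assigned even when the urge to smoke never fell; a flat, ceiling-bound or steadily rising urge is then recorded at 4 minutes, the earliest possible time

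*Protocol*

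**What the plan says.** Protocol 7.3.2.1 defines Emax as "The maximum change from baseline VAS score", calculated as pre-use minus post-use, so a positive value is a fall in urge. TEmax is the time of Emax, and for ties: "If the maximum value occurs at more than one time point, TEmax will be defined as the first time point with this value". SAP 9.1 repeats both definitions; in a tie TEmax "will be defined as the first time point with this value". The baseline "will be the VAS result closest and prior to product use for the respective product", the scale runs from 0 to 100, and ratings are taken "at Time 0 (pre-product use) and at 4, 8, 15, 45, 60, 120, and 240 minutes relative to the start" of controlled use.

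Neither document requires Emax to be positive before a TEmax is derived. By contrast, SAP 8.4 withholds PK parameters, Tmax included, from subjects with fewer than three consecutive quantifiable post-use concentrations.

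Protocol 7.3.2.1 says Urge to Smoke parameters will be compared but does not say which. SAP 9.1 limits the mixed model and p-values to Emax and AUEC0-240. TEmax is therefore only listed and summarised. The UTSP shell for Table 14.2.3.1.3 sets out the Emax statistics, including mean, median, quartiles and 95% CI, and then adds "Similar to above for Temax, AUCECO-240 and Sex = Female and Overall".

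**The concern.** A session with no fall in urge has no time of maximum relief. The rule nevertheless produces one, because Emax is a signed maximum with no lower limit: when every change is zero or negative, the maximum is the tied zero or the smallest rise. If the urge is flat or climbing, this lies at the first rating.

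Such sessions are plausible. Before each controlled use, subjects "abstain from use of any tobacco- or nicotine-containing products for at least 12 hours prior", so the pre-use urge may already be near 100, and only one stick or cigarette is used before the 240-minute rating. The 4-minute value would also be hard to interpret. Ten puffs at 30-second intervals put the tenth puff at 9 × 30 s = 270 s, or 4.5 minutes, so the 4-minute rating comes before the stick is finished.

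At stake is how the onset of craving relief is described for each product under secondary objective 2. Non-response would enter the summary as the fastest response.

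**Working it through.** The plan gives no TEmax figure to reproduce. The check applies the written rule at the SAP 9.1 times (4, 8, 15, 45, 60, 120, 240 min): change at t = VAS pre-use − VAS at t; Emax = largest change; TEmax = its time, the first if tied.

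**Step 1. Fixed profiles.**

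| Profile | Emax | TEmax |
|---|---|---|
| Flat at 80 | 0 | 4 min |
| Constant at the ceiling of 100 | 0 | 4 min |
| Pre-use 70, rising steadily from 71 to 98 | −1 | 4 min |
| Pre-use 70; post-use 75, 75, 80, 85, 90, 95, 100 | −5 | 4 min |
| Rises during use, back to the pre-use value at 45 min, never below it | 0 | 45 min |
| Pre-use 70; post-use 40, 20, 25, 40, 50, 70, 85 | 50 | 8 min |
| Effective, lowest urge at 15 min | 50 | 15 min |

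The tie rule produces the 4 minutes in the flat and ceiling profiles. In the steadily rising one there is no tie; the unrestricted signed maximum is the cause.

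**Step 2. Effect on a summary of 25 sessions.** The shares below are assumptions. Let k sessions have no relief (TEmax 4) and the rest peak at 15 min.

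- Mean = (4k + 15(25 − k))/25, which gives 13.7, 12.8, 11.5, 10.6 and 9.3 min for k = 3, 5, 8, 10 and 13.
- The median is the 13th ordered value: 15 min up to k = 12, and 4 min from k = 13.
- Comparator relieving all 25 (15 sessions at 8 min, 10 at 15 min): mean (15 × 8 + 10 × 15)/25 = 10.8 min, median 8 min.

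At k = 10 the means are almost equal (10.6 and 10.8 min), although one product gave no relief in 10 of 25 sessions. The medians (15 and 8 min) still order the products correctly.

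**Step 3. Noisy ratings without true relief.** If the urge is flat and the pre-use and seven post-use ratings vary independently and alike, P(TEmax ≤ 8 min) = 2/7 = 28.6% and P(Emax ≤ 0) = 1/8 = 12.5%.

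Simulation, 100,000 subjects per scenario. Assumptions, not from the documents: mean urge 70 or 90, between-subject SD 15, rating SD 0.5 to 10 mm, upward drift 0 to 30 mm over 240 min, scores rounded and held within 0 to 100.

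| No true relief | Median TEmax | Share at ≤ 8 min |
|---|---|---|
| Drift 10 to 30 mm, rating SD ≤ 5 | 4 to 8 min | 51% to 100% |
| Drift 10 to 30 mm, rating SD 10 | 8 to 15 min | 41% to 61% |
| Flat at 70, rating SD 5 to 10 | 45 min | 30% to 32% |
| Flat at 90, rating SD 5 / SD 10 | 15 / 45 min | 42% / 36% |

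Simulated effective products had medians of 8 min (lowest urge at 8 min) or 15 min (lowest urge at 15 min).

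**Step 4. How much a condition on Emax catches.** At mean urge 70 and rating SD 2 to 10 mm, Emax was zero or negative in 14% (flat, SD 10) to 49% (drift 30, SD 2) of simulated no-relief subjects. The rest had a small positive Emax by chance.

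**The case against.** The strongest reply is that little depends on TEmax. Under the SAP it has no model and no p-value. The tested parameters, Emax and AUEC0-240, score an ineffective product as ineffective. Emax is in the same summary table and beside TEmax in the subject listing (Appendix 16.2.6.5), so a non-positive Emax is visible. All of this stands and limits the consequence.

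A reader might also infer more than the documents support:

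- *That a product without relief will be recorded as acting within 4 to 8 minutes.* This needs a steady or rising urge and low rating noise. Step 3 gives medians of 15 to 45 minutes for a flat urge with rating SD 5 to 10, and one never-fell profile in step 1 gives 45 minutes.
- *That TEmax is the only measure of speed of relief.* Table 14.2.3.1.2 gives the change from pre-use at each time point by product, and Product Evaluation Scale item 11 asks about immediate relief of craving. TEmax is only the one derived time-to-effect parameter.
- *That the tie rule is the defect.* It is the same convention as for Tmax, and changing it alone would not help a rising urge.
- *That ineffective products will look faster.* In step 2 the medians order correctly at k = 10. Nothing in the documents supports a share as high as 10 or 13 of 25.

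What the reply does not supply is a rule for Emax ≤ 0. The table also has no row showing how many sessions had no relief.

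**Conclusion.** The gap is real and minor. Followed exactly, the rule gives every session with evaluable ratings a TEmax, including sessions where the urge never fell, and for a flat, ceiling-bound or steadily rising urge that value is 4 minutes. Such sessions can pull a product's TEmax summary towards fast onset, the mean first and the median only when they are the majority (under the step 2 assumptions). With noisy ratings the assigned time can be any of the seven, so the direction of the distortion is not fixed.

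The definitions and rating times come from the documents. The share of sessions without relief, the rating noise and the drift are assumptions, so no size can be stated for this trial. No primary result and no planned test is affected.

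**What to change.** State in Protocol 7.3.2.1 and SAP 9.1 that TEmax is not determined ('not reached') when Emax ≤ 0. Add a row to Table 14.2.3.1.3 with n (%) not reached by product, separate from the shell's existing count of missing values so that non-response is not mixed with missing ratings. Summarise TEmax by median and quartiles, read alongside Emax. In the step 2 example with k = 13, the table would show 13/25 = 52% not reached and a median of 15 min among the other 12, in place of a median of 4 min.

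The cost is one sentence in each document, one programming condition and one table row; the mean of TEmax is given up. The median then describes only sessions with an observed fall, so it must be read with the not-reached count. Placing not-reached sessions after 240 minutes when forming the median and quartiles is an optional alternative.

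The remedy is partial. It removes only sessions with no observed fall; a small positive Emax due to rating noise keeps its TEmax. Prespecifying a minimum fall would address that, but the threshold would need its own justification, since the documents offer none.

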7.3.2.2 Product Evaluation Scale

Product Evaluation will be considered as a 7-point scale. Responses will be presented as the following factor scores:

- a) Satisfaction: average of the response scores from questions 1, 2, 3, and 12;
- b) Psychological reward: average of the response scores from questions 4 to 8;
- c) Aversion: average of the response scores from questions 9, 10, 16, and 18;
- d) Relief: average of items 11, 13, 14, 15, and reversed for item 20 (i.e., not at all = 7, extremely = 1);
- e) Items 17, 19, 21 will be summarised as individual item scores.

Descriptive statistics of the subscales will be provided by study product, by sex and overall. Individual responses will be listed by subject.

7.3.2.3 Intent to Use

Descriptive statistics of the VAS will be provided by study product. Individual responses will be listed by subject.

7.3.3 Puff Topography

The following topography parameters will be assessed:

- Puff count

- Puff duration
- Puff volume
- Peak puff flow rate
- Average puff flow rate
- Inter-puff interval

Topography parameters will be listed by subject and summarised by study product, study day, overall and by sex, usual brand cigarette flavour (non-menthol or menthol), age, number of years smoking, CPD, and time point using descriptive statistics.

An appropriate statistical method, similar to the PK analysis detailed above, will be used to compare topography parameters.

7.3.4 Product Use Behaviour

The number of HTP/HHP sticks used (*ad libitum* product use session), the number of CCs smoked (Days -1 through 5), and the number of puffs (morning controlled product use session) will be listed by subject and summarised by study product, product use session, study day and overall using descriptive statistics.

7.3.5 Safety

Safety data including single vital signs assessments, ECGs, and clinical laboratory results will be listed and summarised by subject and time point as appropriate.

All AEs captured in the database will be listed in by-subject data listings. However, only study product use-emergent AEs will be summarised. A study product use-emergent AE is defined as an AE that is starting or worsening at the time of or after the first study product use.

Frequencies of subjects with study product use-emergent AEs, regardless of relationship to study product will be summarised and sorted by system organ class. Frequencies of subjects with study product use-emergent serious AEs will be likewise summarised. Frequencies of study product use-emergent AEs will be summarised by severity and relationship to study product.

Changes in physical examinations (if any) will be described in the text of the final report.

All concomitant medications recorded will be listed by subject.

Incidence of device malfunction(s) will be tabulated.

8. STUDY ADMINISTRATION

8.1 Ethics

8.1.1 Institutional Review Board

This protocol, ICFs, and any amendments to the protocol will be reviewed by a Research Ethics Committee (REC) prior to initiation. The study will not be initiated without the approval from the REC. Notice that the protocol and informed consent that have been reviewed and approved by the REC will be in the final study report.

8.1.2 Ethical Conduct of the Study

This research will be carried out in accordance with the protocol and in accordance with the relevant articles of the Declaration of Helsinki as adopted by the 18th World Medical Assembly in 1964 and as revised in Tokyo (1975), Venice (1983), Hong Kong (1989), South Africa (1996) and Edinburgh (2000); Notes of Clarification added Washington (2002) Tokyo (2004), South Korea (2008), and Brazil (2013).

8.1.3 Subject Information and Consent

The purpose of the study, the procedures to be carried out, and the potential hazards will be described to the subjects in non-technical terms. Subjects will be required to read, sign, and date an ICF summarising the discussion prior to Screening, and will be assured that they may withdraw from the study at any time without jeopardising their medical care.

Subjects will be given a copy of their signed ICF.

8.2 Confidentiality

All clinical sites and vendors will have signed confidentiality agreements with Celerion. By signing this protocol, the Investigator and Celerion staff will regard all information provided by the Sponsor and all information obtained during the course of the study as confidential.

Neither the clinical site nor Celerion will supply to the Sponsor any subject names, initials, date of birth (except year), or other personal identifiers. All such information appearing on any study document must be redacted before a copy of the document is supplied to the Sponsor. The photocopied government-issued ID to verify subject age will be kept separate from other source documentation and not provided to the Sponsor. Study findings stored on a computer will be stored in accordance with local data protection laws. As required, in the case of an event where medical expenses are the responsibility of the Sponsor, personal information i.e., full name, National Insurance Number details etc. may be released to the Sponsor. The subjects will be informed during the consenting process that representatives of the Sponsor, EC, or regulatory authorities may inspect their medical records to verify the information collected, and that all personal information made available for inspection will be handled in the strictest confidence and in accordance with local data protection laws.

8.3 Termination of the Study

The Investigator reserves the right to terminate the study in the interest of subject welfare.

The Sponsor reserves the right to suspend or terminate the study at any time.

8.4 Data Quality Assurance

Standard operating procedures are available for all activities performed at Celerion relevant to the quality of this study. Designated personnel of Celerion will be responsible for implementing and maintaining quality assurance (QA) and quality control systems to ensure that the study is conducted, and that data are generated, documented and reported in compliance with the study protocol, GCP and Good Laboratory Practice requirements as well as applicable regulatory requirements and local laws, rules and regulations relating to the conduct of the clinical study.

The Clinical Study Report will be audited by the QA department and the QA audit certificate will be included in the study report.

All clinical data will undergo a 100% quality control check prior to clinical database lock. Edit checks are then performed for appropriate databases as a validation routine using SAS® or comparable statistical program to check for missing data, data inconsistencies, data ranges, etc. Corrections are made prior to database lock.

8.5 Direct Access to Source Data/Documents

All clinical sites and vendors will ensure that the Sponsor, EC and inspection by domestic and foreign regulatory authorities will have direct access to all study-related sites, source data/documents, and reports for the purpose of monitoring and auditing (ICH[E6][R2] 5.1.2 & 6.10). In the event that other study-related monitoring should be done by other parties, they will be required to sign a confidentiality agreement prior to any monitoring and auditing.

